The primary endpoint will additionally be analyzed using a Cox proportional hazards (CPH) time to event statistical model, if the hazards by treatment group can be assumed proportional using a graphical comparison of log-minus-log survival curves and no more than two-thirds of the recovery times are censored in each treatment group. The CPH model will be used for descriptive purposes, with treatment group and injection site modeled as categorical effects, and baseline plasma glucose modelled as a continuous covariate. The treatment group rate ratios, active versus placebo, will be estimated together with the 95% confidence intervals, and pairwise treatment group inferences (dasiglucagon vs placebo, GlucaGen vs placebo) will be evaluated using two-sided likelihood ratio tests.

Due to the discrete nature of blood sampling in time, and the fact that there must be a true, but unmeasured, ordering of the recovery times, the method using the “exact discrete” partial likelihood for tied failure times will be applied. In SAS, this is implemented in the phreg procedure with the option ties=discrete. The influence of injection site on time to recovery will also be evaluated in the proportional hazards model by a ‘type 3’ test in the phreg procedure.

To obtain an estimate of these true, but unassessed, patient recovery times, a linear interpolation (between the two time points before and after recovery is observed) will be carried out to estimate the patients’ actual time of recovery. These derived recovery times will be described and analysed in the same manner as for the discrete times above.

CONFIDENTIAL

Sponsor:	Zealand Pharma A/S	Protocol Number:	ZP4207-16137
----------	--------------------	------------------	--------------

Table 4-1: Definition of Events, Censoring, and Populations for Time to Event Analyses

Time to Event Endpoint	Initiating Event	Terminating Event(s)	Censoring Event(s) /Competing Risk(s)	Analysis Sample	Study Endpoint /Statistical Analyses
Time to plasma glucose recovery	Administration of IMP	First increase in plasma glucose of ≥ 20 mg/dL (1.1 mmol/L) from baseline w/out rescue IV glucose admin.	Rescue IV glucose administration will be censored at 45 minutes after IMP dosing	Full analysis set, PP	Primary/ Pairwise two-sided log rank test

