3.9 Sample Size

Due to requirements in the size of the safety database, the sample size is set to 78 subjects treated with dasiglucagon 0.6 mg. From phase 2, the median time to an increase of 20 mg/dL of the 0.6 mg dose was approximately 10 minutes. With a 2:1:1 randomization ratio for the three treatments, dasiglucagon 0.6 mg, placebo, and GlucaGen 1 mg, and assuming an exponential time-to-recovery distributions with median times of 10 and at least 20 minutes for dasiglucagon and placebo, respectively, a two-sided log-rank test will be able to detect a difference between dasiglucagon and placebo with 90% power with a follow-up time of 45 minutes at a 5% significance level with 78 subjects treated with dasiglucagon and 39 subjects with placebo. The median time-to-recovery for placebo is expected to be longer than 20 minutes, which means that the power will be greater than 90%.

4 Statistical Methodology

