4.7.1. Hierarchical testing procedure

For the confirmatory analyses, the following a priori defined hierarchical inferential test order will be applied for the control of the type 1 error rate across the planned multiple comparisons. The primary endpoint and key secondary endpoints will be inferentially evaluated within the Full analysis set in the following order, where inference will proceed at the two sided 0.05 criterion significance level until the first failure to reject the null hypothesis for a dasiglucagon versus placebo comparison:

- Primary: Time to plasma glucose recovery
- Key secondaries 1-4: Plasma glucose recovery within 30 minutes, within 20 minutes, within 15 minutes, and within 10 minutes after study drug injection without administration of rescue IV glucose.
- Key secondaries 5-8: Plasma glucose changes from baseline within 30 minutes, within 20 minutes, within 15 minutes, and within 10 minutes after study drug injection or at the time of rescue.

The GlucaGen versus placebo comparisons will not be included in the inferential testing hierarchy, since the efficacy of GlucaGen is previously established, and these comparisons are intended to support the validity of the study for the dasiglucagon versus placebo comparisons.

Analogous supportive sensitivity analyses will be conducted in the PP set, but without inference intent.

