4.12 Subject Withdrawals and Missing Data

Failure is defined for the primary time-to-recovery endpoint as censored with time to recovery set to the maximum follow-up time, here 45 minutes. Individuals will be set to 'failure' in case of receiving rescue IV glucose, discontinuation due to treatment or discontinuation in connection with the induced hypoglycemia state. Only if an intermediate assessment is missing independent of rescue treatment, study treatment or an adverse event including hypoglycemia, a linear interpolation can be applied to impute a missing value.

The same construct of imputation for missing values applies for the analysis of the plasma glucose AUC0-30min.

In the case of subject withdrawal, no imputation of values for PK or PD measurements will be done. Analyses will be done on valid cases only, i.e., no imputation techniques such as last observation carried forward will be applied.

CONFIDENTIAL

Sponsor:	Zealand Pharma A/S	Protocol Number:	ZP4207-16137
----------	--------------------	------------------	--------------

Methods for Handling Missing Dates

All analyses and descriptive summaries will be based on the observed data. For the subject data listings, no imputation of incomplete dates will be applied. The listings will present the incomplete dates without any change.

Missing or Partial Death Dates

- If the entire date is missing, the death date will be imputed as the day after the date of last contact.
- If the day or both day and month is missing, the death date will be imputed to the maximum of the full (non-imputed) day after the date of last contact and the following:
 - If day is missing, day will be 1st of the month
 - If both day and month are missing, death month and day will be January 1st.

Missing Dates in Adverse Events/Concomitant Therapies

Dates missing the day or both the day and month of the year will adhere to the following conventions:

- The missing day of onset of an AE or start date of a therapy will be set to:
 - first day of the month that the event occurred, if the onset yyyy-mm is after the yyyy-mm of first study treatment
 - the day of the first study treatment, if the onset yyyy-mm is the same as yyyy-mm of the first study treatment
 - the date of informed consent, if the onset yyyy-mm is before the yyyy-mm of the first treatment
- The missing day of resolution of an AE or end date of a therapy will be set to:

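### SAP 4.7.2.1 makes the Cox rate ratio conditional and descriptive, while 4.10 makes it unconditional and inferential; under 4.7.2.1 the only between-arm estimate with a CI for the primary endpoint can be dropped when placebo does badly

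*SAP*

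**What the plan says.** SAP 4.7.2.1 evaluates the primary endpoint with a log-rank test stratified by injection site. Kaplan-Meier summaries by arm, a stratified Wilcoxon test and histograms support it. A Cox model is added under two conditions. The first is "if the hazards by treatment group can be assumed proportional using a graphical comparison of log-minus-log survival curves". The second is that "no more than two-thirds of the recovery times are censored in each treatment group". The rate ratios with 95% confidence intervals come from this model, which the section describes as descriptive. The section gives no criterion for judging the curves and names no alternative estimate if either condition fails. The interpolated recovery times are to be handled the same way, so they bring no separate estimate.

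Section 4.10 specifies the same model, covariates, rate ratios, intervals and likelihood ratio tests. It attaches no condition and says the model serves inference. Table 4-2 lists the model for the time-to-recovery analyses, again without a condition.

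On censoring, 4.12 says "Individuals will be set to 'failure' in case of receiving rescue IV glucose", with time set to the maximum follow-up of 45 minutes. Certain discontinuations are treated the same way.

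**The concern.** Two programmers following this SAP could differ on whether a rate ratio is reported at all, and on whether its p-value is inferential.

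If 4.7.2.1 governs, reporting depends on the observed outcome. Censoring here mostly means that the subject did not recover or was rescued, so it is not mainly lost information. The censoring condition is therefore most likely to fail when placebo does worst, which is when the treatment contrast is largest. One failing arm removes the whole model. The placebo Kaplan-Meier median would then not be reached either, because at most 12 of 39 (31%) would have recovered, so a difference in medians could not stand in.

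The curve inspection raises a separate problem. It compares treatment groups, so it takes place after unblinding, and without a rule the decision is open to judgement.

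**Working it through.** **Inputs (SAP 3.9, 4.7.1, 4.7.2.1, 4.12).** The test is two-sided at 5% ("inference will proceed at the two sided 0.05 criterion significance level"). The stated power is "with 90% power with a follow-up time of 45 minutes at a 5% significance level". The arm sizes are 78 for dasiglucagon and 39 for placebo. Recovery times are taken as exponential with "median times of 10 and at least 20 minutes for dasiglucagon and placebo, respectively".

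**Reproducing the stated power.** The expected proportion of events by 45 minutes is 1 − 2^(−45/median).
- Dasiglucagon: 78 × (1 − 2^(−4.5)) = 74.6.
- Placebo: 39 × (1 − 2^(−2.25)) = 30.8.
- Total: 105.4 events.
- Schoenfeld: √(105.4 × 2/3 × 1/3) × ln 2 − 1.96 = 1.39, giving 91.8% power.
- Using variance 1/74.6 + 1/30.8 for the log rate ratio: 89.9%.
- Simulated unstratified log-rank test, 2,000 runs: 90.4%.

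The stated 90% is sound, and these inputs can be used for the next step.

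**When the censoring condition fails for placebo.** 26 of 39 censored is exactly two-thirds and passes; 27 of 39 (69%) fails. Failure therefore means 12 or fewer recoveries.

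**Chance of failure.** With placebo median m, the censored share at 45 minutes is q = 2^(−45/m), and the chance is P(X ≥ 27) for X ~ Binomial(39, q). The SAP gives no placebo median beyond 20 minutes, so the other rows are assumptions.

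| Placebo median (min) | Censored share | Chance the condition fails |
|---|---|---|
| 20 (planning value) | 21% | about 0% |
| 40 | 46% | 0.3% |
| 60 | 60% | 14% |
| 77 | 67% | 44% |
| 90 | 71% | 66% |
| 120 | 77% | 91% |

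The expected share reaches two-thirds at m = 45 × ln 2 / ln 1.5 = 76.9 minutes.

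**Sensitivity.**
- No extra censoring from rescue is included above. By total censored share, whatever its cause, the chance is 1.2% at 50%, 15.5% at 60%, 35.5% at 65%, 61.8% at 70%, 84.6% at 75% and 96% at 80%.
- The last planned sample before 45 minutes is at 40. If recovery can be seen only up to then, the crossover falls to 68.4 minutes, and the chances at medians of 60, 90 and 120 become 26%, 79% and 96%.

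**The three places side by side.**

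| Place | Condition | Role |
|---|---|---|
| 4.7.2.1 | Curves look proportional and at most two-thirds censored per arm | Descriptive |
| 4.10 | None | Inferential |
| Table 4-2 | None | Not stated |

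**The case against.** The strongest reply is that 4.10 and Table 4-2 specify the model without conditions, so on those texts the rate ratio is always reported. This stands against an unqualified reading that the SAP produces the estimate only if both conditions pass; the document as a whole does not say that. It does not settle the matter, because 4.7.2.1 is the section that defines the primary analysis and it does impose them.

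A reader might also infer that a failed condition leaves a bare p-value. The documents do not support this. Kaplan-Meier estimates by arm and recovery proportions within 10, 15, 20 and 30 minutes would still be reported, as would least-squares mean contrasts of glucose change and a glucose AUC ratio with 95% CI. What would be missing is narrower: a between-arm contrast with an interval on the primary endpoint's own time scale.

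A charge of selective reporting would go too far as well. The two-thirds limit is a fixed number set in a plan due for approval before unblinding; only the curve inspection involves judgement.

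Finally, at the planning median of 20 minutes the censoring condition practically never fails, and near-even odds need a median almost four times as long. That is correct. However, 3.9 treats 20 minutes as a floor: "The median time-to-recovery for placebo is expected to be longer than 20 minutes". It offers no upper figure or expected rescue rate, so the risk cannot be dismissed from the document.

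**Conclusion.** The point holds as an inconsistency between 4.7.2.1, 4.10 and Table 4-2 on whether the Cox estimate is conditional, and between 4.7.2.1 and 4.10 on its role. The consequence is that, if 4.7.2.1 is followed, the estimate can be lost on observed outcomes with no replacement named.

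The chance of loss through the censoring condition runs from about 0% to 91% over placebo medians of 20 to 120 minutes. That is a range under assumed exponential times, not a forecast. The chance of loss through the curve inspection cannot be calculated, because no criterion is given.

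The stratified log-rank test, its type I error and the testing hierarchy do not depend on the Cox model. This is worth correcting before unblinding, but it does not threaten the primary conclusion.

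**What to change.** Reconcile 4.7.2.1, 4.10 and Table 4-2 so that all three say the same thing:
- The Cox rate ratio with 95% CI is always reported as a descriptive, supportive estimate outside the testing hierarchy. Its likelihood ratio p-values are labelled nominal.
- Both conditions are removed. The log-minus-log plot is kept as a diagnostic that informs interpretation and does not decide reporting.
- One estimate that does not need proportional hazards is prespecified. The dasiglucagon minus placebo difference in restricted mean time to recovery up to 45 minutes, with 95% CI, would serve. It works when medians are not reached and matches the rule in 4.12 that failures are carried to 45 minutes. Other choices, such as the difference in proportion recovered by 45 minutes, are also acceptable.
- The 45-minute horizon is stated explicitly for this estimate, because 4.7.2 also lists the 50- and 60-minute samples for analysis while 4.12 gives 45 minutes as maximum follow-up.

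The cost is SAP wording and one extra table line from data already collected. The only downside is one more number to report.

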4.7.2. Primary endpoint

- Time to plasma glucose recovery. Plasma glucose recovery is defined as first increase in plasma glucose of ≥ 20 mg/dL (1.1 mmol/L) from baseline during the hypoglycemic clamp procedure without administration of rescue IV glucose.

The planned time points at 0, 6, 8, 10, 12, 15, 17, 20, 25, 30, 40, 50 and 60 minutes will be used in the analyses.

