4.10 Adjustment for Covariates

The primary endpoint will be additionally analyzed using a Cox Proportional Hazards (CPH) time to event statistical model. The CPH model will be used for inferences, with treatment group and injection site (abdomen, buttock, or thigh) modelled as categorical effects, and baseline plasma glucose modelled as a continuous covariate. The treatment group rate ratios, active versus placebo, will be estimated together with the 95% confidence intervals, and pairwise

CONFIDENTIAL

Sponsor:	Zealand Pharma A/S	Protocol Number:	ZP4207-16137
----------	--------------------	------------------	--------------

treatment group inferences (dasiglucagon vs placebo, GlucaGen vs placebo) will be evaluated using two-sided likelihood ratio tests.

The key secondary endpoints of plasma glucose changes from baseline changes from baseline within 30 minutes, within 20 minutes, within 15 minutes, and within 10 minutes after study drug injection or at the time of rescue, will be analyzed with the plasma glucose changes from baseline at rescue carried forward in those subjects who require rescue IV glucose before plasma glucose ≥ 20 mg/dL recovery. Each of these changes from baseline variables will be analyzed using an Analysis of Covariance model, with treatment group modelled as a fixed effect and with the baseline plasma glucose modelled as a covariate. The dasiglucagon versus placebo treatment group difference will be evaluated inferentially as a least squares means contrast, using a two-sided t-test at the 0.05 significance level, first for the 30 minute changes from baseline, and then sequentially for the 20 minute, 15 minute, and 10 minute variables, until the first failure to reject.

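### The Cox model's ties=discrete option contradicts the SAP's own rationale and yields a discrete-time odds ratio labelled a rate ratio, about 8% too high at the planning effect

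*SAP*

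**What the plan says.** SAP section 4.7.2.1 adds a Cox model to the log-rank analysis of the primary endpoint, with treatment and injection site as factors and baseline glucose as a covariate. What it will report is stated plainly: "The treatment group rate ratios, active versus placebo, will be estimated together with the 95% confidence intervals".

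The reason given for the handling of ties is that sampling is discrete but "there must be a true, but unmeasured, ordering of the recovery times". On that basis, "the method using the “exact discrete” partial likelihood for tied failure times will be applied", and "In SAS, this is implemented in the phreg procedure with the option ties=discrete". The next paragraph again treats the true times as continuous: recovery times are interpolated between samples and analysed in the same way as the grid times.

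The grid is in section 4.7.2: "The planned time points at 0, 6, 8, 10, 12, 15, 17, 20, 25, 30, 40, 50 and 60 minutes".

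On the model's role, section 4.7.2.1 says "The CPH model will be used for descriptive purposes". It fits the model only if the log-minus-log curves look proportional and "no more than two-thirds of the recovery times are censored in each treatment group". Section 4.10 describes the same model with neither condition and says "The CPH model will be used for inferences".

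**The concern.** Continuous times whose order is hidden by the sampling scheme are the setting of the exact marginal likelihood, which is ties=exact in PHREG. The option named in the SAP rests on the opposite assumption, that tied events really happened together. It fits a discrete logistic model, and its exponentiated coefficient is an odds ratio for recovering in an interval among those still at risk. When the true ratio exceeds 1, that odds ratio exceeds the rate ratio, so the error favours the active arm whenever the drug works.

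Two things are at stake. The effect size for the primary endpoint would be mislabelled and somewhat too favourable. In addition, the grid-time and interpolated-time Cox results would carry the same label while estimating different quantities: interpolated times should have few ties, so their estimate should lie close to a true rate ratio.

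Separately, the two sections give the model different standing and different conditions for use.

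**Working it through.** **Inputs.** From SAP section 3.9: 78 dasiglucagon and 39 placebo subjects, exponential recovery times, medians of 10 and 20 minutes (rate ratio 20/10 = 2), 45 minutes of follow-up, two-sided 5% log-rank test, 90% power. From section 4.7.2: sampling times 6, 8, 10, 12, 15, 17, 20, 25, 30 and 40 minutes before the 45-minute cut. Injection site and baseline glucose are left out of the calculations.

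**The plan's own power figure.** Expected events = 78(1 − 2^−4.5) + 39(1 − 2^−2.25) = 74.6 + 30.8 = 105.4. By Schoenfeld's formula, √(105.4 × 2/3 × 1/3) × ln 2 − 1.96 = 3.35 − 1.96 = 1.39, which is a power of 91.8%. The simulated log-rank power is 91.0% on continuous times and 89.4% on the grid. The stated 90% is reproduced.

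**How heavy the ties are.** Expected recoveries first seen at 6 minutes are 78(1 − 2^−0.6) + 39(1 − 2^−0.3) = 26.5 + 7.3 = 33.9. Each later sample to 40 minutes has between 5 and 9.

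**What the discrete model estimates in each interval.** For an interval of w minutes, the odds of recovery are 2^(w/10) − 1 on dasiglucagon and 2^(w/20) − 1 on placebo. Their ratio is 1 + 2^(w/20), which is above 2 for every w > 0.

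| Interval width (min) | Odds ratio at true rate ratio 2 |
|---|---|
| 2 | 2.07 |
| 3 | 2.11 |
| 5 | 2.19 |
| 6 | 2.23 |
| 10 | 2.41 |

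**Large-sample value.** With n1 and n0 at risk and d1 and d0 recovering in each interval, the estimate β solves Σ[d1 − n1·expit(c + β)] = 0. In each interval, c is set so that n1·expit(c + β) + n0·expit(c) = d1 + d0. The dasiglucagon median is held at 10 minutes.

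| Placebo median (min) | True rate ratio | ties=discrete | Inflation |
|---|---|---|---|
| 20 | 2 | 2.17 | 8% |
| 30 | 3 | 3.35 | 12% |
| 40 | 4 | 4.53 | 13% |

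**At the trial's size.** Geometric means over 1,000 simulated trials of 78 against 39, at a true rate ratio of 2: 2.16 with ties=discrete, 2.00 with ties=exact, 1.99 with Efron and 1.85 with Breslow.

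**Sensitivity to an assumption outside the SAP.** If recoveries cluster around 10 minutes (Weibull, same dasiglucagon median), the inflation at a rate ratio of 2 is 12% (shape 2) to 17% (shape 3). At a rate ratio of 4 it is 22% to 31%.

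**Effect on testing.** The likelihood ratio test rejects in 4.9% of trials (discrete) against 5.2% (exact) at a rate ratio of 1. At a rate ratio of 2 it rejects in 89.7% against 89.5%.

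**The case against.** The confirmatory result does not depend on this model. The primary test is the log-rank test stratified by injection site, the hierarchy in section 4.7.1 does not name the Cox model, and the likelihood ratio test behaves alike under either option. All of this stands. At the planning effect the distortion is also modest: the log shift is ln 1.084 = 0.08, against a standard deviation of about 0.26 for the log estimate in simulation, or roughly 0.3 standard errors.

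The SAP's named likelihood and its code do agree with each other, and discrete sampling is a fair description of the data. The conflict is with the clause on unmeasured ordering and with the rate-ratio label, so relabelling is as valid a repair as changing the option.

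A reader might infer three stronger things that the SAP does not support:

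- That this is the only between-group effect estimate for the primary endpoint. The Cox analysis of interpolated times is a second one, with few ties expected.
- That inflation of 20% to 30% should be expected. That needs both a rate ratio near 4 and Weibull clustering that the SAP does not state.
- That the two-thirds censoring condition will suppress the estimate when the drug works best. With exponential times and no separate model of rescue, the chance that more than 26 of 39 placebo subjects are unrecovered at 45 minutes is under 10^−9 at a placebo median of 20 minutes, 0.3% at 40 and 14% at 60. It reaches 50% only at 80 minutes. The SAP says at least 20 and expects longer, but gives no such figure. Rescue could raise these chances. Even so, declining to fit a Cox model with few events in an arm is a defensible prespecified choice.

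**Conclusion.** The rationale, the option and the label in section 4.7.2.1 cannot all be right, so the text is wrong as written and should be fixed. On the SAP's grid with exponential times and a 10-minute dasiglucagon median, ties=discrete overstates the rate ratio by about 8% at 2 and about 13% at 4. Larger figures rest on the added clustering assumption. The problem is confined to the reported estimate, its confidence interval and its comparability with the interpolated-time result; it does not threaten the trial's confirmatory conclusion.

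The disagreement between sections 4.7.2.1 and 4.10 on the model's role and on its conditions for fitting is a real contradiction in the text, whichever tie method is kept.

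**What to change.** In section 4.7.2.1, replace ties=discrete with ties=exact and correct the sentence that names the likelihood. Alternatively, keep ties=discrete, label the result a discrete-time odds ratio, and rewrite the rationale so that it no longer appeals to an unobserved ordering. In that case the grid-time and interpolated-time tables need different labels.

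In section 4.10, describe the Cox model as supportive or descriptive, in line with section 4.7.2.1, and state the same conditions for fitting it in both places.

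The cost is one SAS option and a few sentences. With ties=exact, the sponsor accepts a slightly less favourable estimate. Dropping the fitting conditions or adding a difference in restricted mean time to recovery would be a matter of preference and is not needed to correct the error.
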